4.2.2 Primary Endpoint – 6MWD change from baseline at 16 weeks

4.2.2.1 Definition

The other dual primary efficacy endpoint is 6MWD change from baseline at 16 weeks. For this endpoint, the same estimands will be used as for the analysis of KCCQ-TSS change from baseline at 16 weeks described in Sections 4.2 and 4.2.1.

4.2.2.2 Derivations

The absolute change from baseline at 16 weeks will be derived.

4.2.2.3 Handling of Dropouts and Missing Data

See Section 4.2.1.3 for details.

4.2.2.4 Primary Analysis of Primary Endpoint

See section 4.2.1.4 for details.

4.2.2.5 Sensitivity Analyses of the Primary Endpoint

See Section 4.2.1.5 for details.

4.2.2.6 Supplementary Analyses of the Primary Endpoint

See Section 4.2.1.6 for details. For the fourth supplementary analysis, the ANCOVA model will include treatment group and neutrophil count stratum as categorical covariates, and the baseline value as continuous covariate. The figure described for the KCCQ-TSS fourth supplementary analysis in Section 4.2.1.6 will not be presented for this analysis.

4.2.2.7 Subgroup Analyses

See Section 4.2.1.7 for details.

4.2.3 Secondary Endpoints – KCCQ-TSS change from baseline at 24 and 48 weeks

4.2.3.1 Definition

KCCQ-TSS change from baseline at 24 and 48 weeks respectively are secondary endpoints.

4.2.3.2 Derivations

The absolute change from baseline at 24 and 48 weeks respectively will be derived. See Section 4.2.1.2 for derivation of KCCQ-TSS.

4.2.3.3 Handling of Dropouts and Missing Data

See Section 4.2.1.3 describing handling of missing data for the ANCOVA estimator for details.

4.2.3.4 Primary Analysis of Secondary Endpoint

See part of Section 4.2.1.4 for details on the statistical inference. In addition, distribution of KCCQ-TSS at baseline, 12, 16, 24 and 48 weeks respectively will be presented as summary statistics.

The same hypothesis as in section 4.2.1.4 will be tested. See Section 3.3.4 for details on the hierarchical testing sequence.

4.2.4 Secondary Endpoint – 6MWD change from baseline at 24 and 48 weeks

4.2.4.1 Definition

6MWD change from baseline at 24 and 48 weeks respectively are secondary endpoints.

4.2.4.2 Derivations

The absolute change from baseline at 24 and 48 weeks respectively will be derived.

4.2.4.3 Handling of Dropouts and Missing Data

See part of Section 4.2.1.3 describing handling of missing data for the ANCOVA estimator for details.

4.2.4.4 Primary Analysis of Secondary Endpoint

See part of Section 4.2.1.4 for details on the statistical inference. In addition, summary statistics will be shown, as described in Section 4.2.2.4.

The same hypothesis as in section 4.2.1.4 will be tested. See Section 3.3.4 for details on the hierarchical testing sequence.

4.2.5 Secondary Endpoints – Change from baseline in log-transformed NT-proBNP at 16, 24 and 48 weeks

4.2.5.1 Definition

Change from baseline in log-transformed NT-proBNP at 16, 24 and 48 weeks respectively are secondary endpoints.

4.2.5.2 Derivations

The change from baseline in log-transformed NT-proBNP at 16, 24 and 48 weeks respectively will be derived.

4.2.5.3 Handling of Dropouts and Missing Data

See part of Section 4.2.1.3 describing handling of missing data for the ANCOVA estimator for details.

4.2.5.4 Primary Analysis of Secondary Endpoint

The analysis is evaluated under the primary estimand defined in Section 4.2, using ANCOVA as estimator, comparing AZD4831 Total versus placebo.

The change from baseline in log-transformed NT-proBNP is the response variable in the ANCOVA model with the same covariate model specification as in Section 4.2.1.4, but with a log-transformed baseline value. The endpoint will be analysed on a natural logarithmic scale and then back transformed to the original scale resulting in geometric means.

The change from baseline in log-transformed NT-proBNP is tested in the hypothesis testing procedure. See Section 3.3.4 for details on the hierarchical testing sequence.

Geometric mean estimates for each treatment group, geometric mean ratios between treatment groups, 95% CIs and p-value will be presented. In addition, distribution of NT-proBNP at baseline, 16, 24 and 48 weeks respectively will be presented as summary statistics including geometric mean, geometric CV, and geometric mean ratio.

4.2.5.5 Supplementary Analyses of the Secondary Endpoint

The supplementary analysis for this endpoint will be evaluated under the third supplementary estimand defined in Section 4.2 using ANCOVA. See Section 4.2.5.4 for details.

4.2.5.6 Subgroup Analysis

A subgroup analysis will be performed for the 16 weeks analysis timepoint. See Section 4.2.1.7 for details. The following variables listed for primary endpoints will not be included: Alcohol consumption, Nicotine consumption, S-Cystatin-C and Ceruloplasmin.

4.2.6 Secondary Endpoints – Echocardiographic parameters change from baseline at 16 and 24 weeks

4.2.6.1 Definition

LV-GLS, LAVI and LVMI change from baseline at 16 and 24 weeks respectively are secondary endpoints.

4.2.6.2 Derivations

The absolute change from baseline at 16 and 24 weeks respectively will be derived.

4.2.6.3 Handling of Dropouts and Missing Data

See part of Section 4.2.1.3 describing handling of missing data for the ANCOVA estimator for details.

4.2.6.4 Primary Analysis of Secondary Endpoint

See part of Section 4.2.1.4 for details on the statistical inference. The same hypothesis as in section 4.2.1.4 will be tested. See Section 3.3.4 for details on the hierarchical testing sequence. In addition, summary statistics will be shown, as described in Section 4.2.3.4.

4.2.6.5 Supplementary Analyses of the Secondary Endpoint

Supplementary analyses of LV-GLS, LAVI and LVMI change from baseline at 16 weeks will be evaluated under the third supplementary estimand defined in Section 4.2 using ANCOVA. See Section 4.2.1.6 for details.

4.2.6.6 Subgroup Analysis

Subgroup analyses will be performed for the 16 weeks analysis timepoint. See Section 4.2.1.7 for details. The following variables listed for primary endpoints will not be included: Alcohol consumption, Nicotine consumption, S-Cystatin-C and Ceruloplasmin.

4.2.7 Secondary Endpoint – Plasma Concentrations of AZD4831 by timepoint

4.2.7.1 Definition

The endpoint is plasma concentration.

4.2.7.2 Derivations

Plasma concentrations of AZD4831 by assessment timepoint will be derived. The number of observations below LLoQ will be presented and will be imputed to LLoQ/2 in the analyses.

4.2.7.3 Handling of Dropouts and Missing Data

Any missing data will not be imputed.

4.2.7.4 Primary Analysis of Secondary Endpoint

Plasma AZD4831 concentrations will be summarised by descriptive statistics for the full analysis set, by assessment timepoints and dose level.

4.2.8 Secondary Endpoint – Change from baseline in log-transformed inflammatory biomarkers at 16, 24 and 48 weeks

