7 DISCONTINUATION OF STUDY INTERVENTION AND PARTICIPANT DISCONTINUATION/WITHDRAWAL

7.1 Discontinuation of Study Intervention

It may be necessary for a participant to permanently discontinue (definitive discontinuation) study intervention. If study intervention is permanently discontinued, the participant should remain in the study, ie, continue to participate in scheduled study visits and evaluations.

Note that discontinuation from study intervention is NOT the same thing as a withdrawal from the study. For procedures in the case of withdrawal from the study, see Section 7.2.

At each visit, participants will be instructed to contact the investigator immediately, if rash or skin reaction has developed. If maculopapular rash grade 1, 2, or 3 has developed, participant must be permanently discontinued from the study intervention and AZ medical staff should be informed.

- Grade 1: Macules/papules covering < 10% Body Surface Area with or without symptoms (eg, pruritus, burning, tightness).

- Grade 2: Macules/papules covering 10 - 30% Body Surface Area, with or without symptoms (eg, pruritus, burning, tightness); limiting Instrumental ADL (refer to preparing meals, shopping for groceries or clothes, using the telephone, managing money, etc); rash covering > 30% Body Surface Area with or without mild symptoms.
- Grade 3: Macules/papules covering > 30% Body Surface Area, with moderate or severe symptoms; limiting Self-care ADL (refer to bathing, dressing and undressing, feeding self, using the toilet, taking medications, and not bedridden).

If the participant develops a rash or skin reaction that is not considered a maculopapular rash, but is a generalised rash/skin reaction or is considered to be an SAE, the participant must be permanently discontinued from the study intervention and AZ medical staff should be informed.

For further information and skin reaction evaluation guidance, see Appendix B 5.

Study participants also may be discontinued from study intervention in the following situations:

- Participant decision. The participant is at any time free to discontinue treatment, without prejudice to further treatment.
- Adverse Event or other safety reasons as judged by the Investigator and/or sponsor where continued treatment may put the participant at undue risk.
- Development of uncontrolled and clinical significant **CCI** as judged by the Investigator.
- Severe non-compliance with the CSP.
- Pregnancy

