4.1.2 Analysis Sets

4.1.2.1 Definitions and Derivations

Full analysis set

All subjects who have been randomised to study treatment and who have received at least one dose of investigational product will be included in FAS irrespective of their protocol adherence and continued participation in the study. Subjects will be analysed according to their randomised

study medication assignment, irrespective of the treatment actually received. FAS is considered the primary analysis set for the primary and secondary efficacy variables as well as for the exploratory efficacy variables.

Safety analysis set

SAS consists of all subjects who have received at least one dose of IP. Erroneously treated subjects (e.g., those randomised to treatment A but actually given treatment B) are accounted for in the treatment group of the treatment they actually received. A subject who has received any dose of the active IP will be classified as in the active IP treatment group. A subject who has received both doses of active IP will be classified as in the highest dose treatment group. SAS is used for all safety analyses.

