Primary analysis of secondary endpoints targeting primary estimand	LVMI change from baseline at 16 and 24 weeks	Principal stratum of FAS	Treatment policy strategy combined with principal stratum strategy	Difference in adjusted mean change from baseline at 16 and 24 weeks (ANCOVA),	4.2.6.4
Supplementary analysis of secondary endpoints targeting third supplementary estimand	LVMI change from baseline at 16 weeks	Principal stratum of FAS	Treatment policy strategy combined with principal stratum strategy	Difference in adjusted mean change from baseline at 16 weeks (ANCOVA)	4.2.6.5
Subgroup analysis of secondary endpoint targeting primary estimand	LVMI change from baseline at 16 weeks	Principal stratum of FAS	Treatment policy strategy combined with principal stratum strategy	Difference in adjusted mean change from baseline at 16 weeks (ANCOVA)	4.2.6.6
Objective 9: To assess the pharmacokinetics of AZD4831					
Primary analysis of secondary endpoints targeting primary estimand	Plasma Concentrations of AZD4831	SAS	Treatment policy strategy	Summary statistics	4.2.7.4
Objective 10: To evaluate the effect of AZD4831 on inflammatory biomarkers					
Primary analysis of secondary endpoints targeting primary estimand	Change from baseline in log-transformed hsCRP and IL-6 at 16, 24, and 48 weeks	Principal stratum of FAS	Treatment policy strategy combined with principal stratum strategy	Adjusted geometric mean ratio between baseline and 16, 24 and 48 weeks (ANCOVA)	4.2.8.4
Supplementary analysis of secondary endpoint targeting third	Change from baseline in log-transformed IL-6 at 16 weeks	Principal stratum of FAS	Treatment policy strategy combined with principal stratum strategy	Adjusted geometric mean ratio between baseline and 16, 24 and 48 weeks (ANCOVA)	4.2.8.5

Statistical category	Endpoint	Population	Handling of intercurrent events	Population level summary (analysis)	Details in section
Primary analysis of exploratory endpoints targeting primary estimand	CCI [REDACTED] [REDACTED] [REDACTED]	Principal stratum of FAS	Treatment policy strategy combined with principal stratum strategy	CCI [REDACTED] [REDACTED] [REDACTED] [REDACTED]	4.2.11.4
CCI [REDACTED] on aspects of the 6MWT, other than the 6MWD					
Primary analysis of exploratory endpoints targeting primary estimand	CCI [REDACTED] [REDACTED] [REDACTED] [REDACTED] [REDACTED] [REDACTED] [REDACTED] [REDACTED]	FAS	Treatment policy strategy	CCI [REDACTED]	4.2.12.3

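### Plasma concentrations are assigned to two different analysis sets in the SAP, and no rule keeps samples taken after stopping drug out of the summaries by dose level

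*SAP*

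**What the plan says.** Plasma concentration of AZD4831 by timepoint and dose level is a Part A secondary endpoint (Protocol 3.1, Table 4; Protocol 9.4.2.2).

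- **Analysis set, first place.** The Objective 9 row of SAP Table 2 reads "Plasma Concentrations of AZD4831 SAS Treatment policy strategy Summary statistics". It is labelled as targeting the primary estimand and points to 4.2.7.4.
- **Analysis set, second place.** SAP 4.2.7.4 says "Plasma AZD4831 concentrations will be summarised by descriptive statistics for the full analysis set, by assessment timepoints and dose level".
- **Grouping rules (SAP 4.1.2.1).** FAS subjects are analysed by randomised "study medication assignment, irrespective of the treatment actually received". In the SAS, wrongly treated subjects are "accounted for in the treatment group of the treatment they actually received". The SAS also has this rule: "A subject who has received both doses of active IP will be classified as in the highest dose treatment group".
- **Values below the quantification limit (SAP 4.2.7.2).** They are counted and "will be imputed to LLoQ/2 in the analyses". Missing values are not imputed (4.2.7.3).
- **After stopping drug (Protocol 7.1).** "If study intervention is permanently discontinued, the participant should remain in the study, ie, continue to participate in scheduled study visits and evaluations".
- **Sampling (Protocol 1.3, Table 1, and footnote g).** PK blood is drawn at Weeks 0, 4, 12, 16, 24, 48 and 52. A sample is also due at the discontinuation visit after rash.
- **Dosing records (Protocol 6.4).** Start and stop dates of study drug go into the eCRF, and a dosing card captures the last dose taken the day before the clinic visit.

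**The concern.** A table of concentration by dose level is read as a description of exposure in people taking that dose. Two features of the SAP interfere with that reading.

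First, a programmer following Table 2 and one following 4.2.7.4 would file a wrongly dosed subject's samples under different doses.

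Second, nothing in 4.2.7 separates samples taken on drug from those taken after permanent discontinuation. The dilution need not be equal across arms or visits. Maculopapular rash of any grade leads to permanent discontinuation (Protocol 7.1), and in the earlier studies rash was reported mainly at the higher doses (Protocol 4.3). If that pattern recurs, the 5 mg summary would be diluted more than the 2.5 mg summary, and later visits more than early ones. The apparent exposure ratio between doses would then partly reflect who stopped.

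**Working it through.** The documents give no concentration, quantification limit or discontinuation rate, so there is no plan figure to reproduce. The text can be compared directly. The size can only be illustrated.

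**Step 1: which set.** Table 2 says SAS and 4.2.7.4 says FAS. The SAP amendment history records that version 3 added the FAS to the PK analysis, so the likely explanation is that the table was not updated. Both sets require at least one dose, so they differ in how wrongly treated subjects are grouped. Let *m* be the share of an arm that took the other active dose, and assume concentration is proportional to dose:

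- 2.5 mg arm by randomisation: mean ratio = (1 − m) + 2m. At m = 0.5% to 2% this is 1.005 to 1.02.
- 5 mg arm by randomisation: mean ratio = (1 − m) + 0.5m. At m = 0.5% to 2% this is 0.9975 to 0.99.

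The shift is small, and its sign depends on the error made.

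**Step 2: are off-drug samples retained?** Discontinued participants attend scheduled evaluations (Protocol 7.1), and PK is one of them (Protocol Table 1). Treatment policy, as the primary estimand in SAP 4.2 implements it, ignores discontinuation and uses all available data. Sections 4.2.7.1 to 4.2.7.4 contain no exclusion. Retention therefore follows from the text, although no sentence states it. The Week 0 pre-dose and Week 52 samples are off drug by design and have their own timepoints, so they do not affect the on-treatment visits (Weeks 4, 12, 16, 24 and 48).

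**Step 3: size at one on-treatment visit.** Assumptions: a share *d* of samples is off drug and below the limit, *R* is the on-drug geometric mean divided by the limit, and on-drug values are log-normal with log-SD 0.5. The on-drug arithmetic mean in units of the limit is then A = R × exp(0.5²/2).

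- Arithmetic mean ratio = 1 − d + 0.5d/A
- Geometric mean ratio = (0.5/R)^d
- Median ratio = exp(0.5 × z), where z is the standard normal quantile at (0.5 − d)/(1 − d)

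| d | Arithmetic mean, R = 5 to 100 | Geometric mean, R = 5 to 100 | Median |
|---|---|---|---|
| 5% | 0.954 to 0.950 | 0.89 to 0.77 | 0.968 (z = −0.066) |
| 10% | 0.909 to 0.900 | 0.79 to 0.59 | 0.933 (z = −0.140) |

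The arithmetic mean hardly depends on *R*; it falls roughly by *d*. The geometric mean depends strongly on *R*, which is unknown. The median falls by about 3% and 7% here, less than either mean, but its fall grows with the assumed spread.

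The only figure in the protocol near *d* is 660 randomised against about 600 with complete safety data (1 − 600/660 = 9.1%). That is a rough proxy at best, because it counts incomplete follow-up and not time off drug.

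**The case against.** Several points on the other side carry weight.

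- **The assay may exclude these samples.** Protocol 6.3 limits bioanalysis to participants on active treatment, which could mean still taking it. The same paragraph says the laboratory selects samples through the treatment codes, which identify the arm and not whether someone has stopped. Protocol 8.5.1.1 sets aside only placebo samples. The better reading is that off-drug samples from active arms are assayed, but the text is ambiguous.
- **A lower mean is what treatment policy describes.** This is correct. Measured against the strategy in Table 2 the summary is not biased; it falls short of concentration while taking the drug. The point is that the on-drug quantity is the more useful target for a summary by dose level. The SAP already offers an on-treatment view for safety (4.6) and an analysis excluding discontinued subjects for NT-proBNP, echocardiographic parameters and IL-6. PK has neither.
- **Readers will have clues.** The median and quartiles are standard output, geometric means appear only where appropriate (SAP 3.3.1.7), and the count below the limit is shown. This limits the harm but does not identify which low values are off drug.
- **Modelling is separate.** Any population PK or PK/PD work has its own data analysis plan (Protocol 9.4.2.2), which may handle these samples. That plan is not available here.

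A reader might infer three stronger things that the documents do not support. The FAS/SAS mismatch does not itself push concentrations down (Step 1). Substituting half the limit is not the cause either: it applies only to results below the limit and gives a higher value than zero, and it is retention of the samples that lowers the summary. Nor is this endpoint shown to drive the Part B dose choice, since Protocol 4.3 lists safety, symptoms, function and other biomarker or efficacy endpoints without naming plasma concentration.

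**Conclusion.** Two separate defects stand, both minor.

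The SAP names two analysis sets for one secondary endpoint. They must be reconciled, but only wrongly treated subjects are affected and the direction is not fixed.

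As written, the by-dose summary at on-treatment visits would also mix on-drug and post-discontinuation samples. Relative to concentration in participants taking the dose, the arithmetic mean would be lower by roughly the off-drug share: about 5% at 5% off drug and 9–10% at 10%. These shares are assumptions, as is the premise that off-drug samples are assayed and fall below the limit. The larger fall in a geometric mean cannot be sized from the documents. The summary is descriptive and outside the testing hierarchy in SAP 3.3.4, so no formal inference is affected.

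Resolving the first defect does not resolve the second. Moving to the SAS would leave every off-drug sample in place, and its highest-dose rule for subjects who received both active doses can itself mix doses.

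**What to change.** 1. Name one analysis set in both Table 2 (Objective 9) and 4.2.7.4, with samples grouped by the dose actually received. Say how subjects who received both active doses are shown, for example listed separately.
2. Restrict the by-dose, by-visit summary to samples taken while on study drug, using the recorded stop dates and last-dose dates. Define the window for PK explicitly. The safety on-treatment period runs to 14 days after the last dose (SAP 3.3.1.5) and should not be borrowed without justification. Cover temporary interruptions in the same rule.
3. List post-discontinuation samples separately, including those from the discontinuation visit after rash, with time since last dose.
4. Replace the treatment-policy entry in the Objective 9 row with wording that matches this target, and clarify in Protocol 6.3 whether samples from participants who have stopped active drug are assayed.

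The cost is SAP wording, one clarifying phrase in the protocol and a date filter on data already collected. Slightly fewer samples will contribute at each visit.

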4.2.8.1 Definition

Change from baseline in log-transformed hsCRP and IL-6 at 16, 24 and 48 weeks respectively are secondary endpoints.

4.2.8.2 Derivations

Change from baseline in log-transformed hsCRP and IL-6 at 16, 24 and 48 weeks respectively will be derived.

If an IL-6 observation is reported with highly sensitive (hs) IL-6 lab code, this data will be included in analysis. Otherwise, the non-hs IL-6 lab code will be used.

Observations reported as LLoQ will be imputed as described in Section 3.3.1.3.

The dichotomous response variable for the logistics regression for IL-6 at 16, 24 and 48 weeks respectively is categorised as

- <3.16
- ≥ 3.16

where 3.16 is the LLoQ reported for the non-hs analysis method first used.

4.2.8.3 Handling of Dropouts and Missing Data

See part of Section 4.2.1.3 describing handling of missing data for the ANCOVA estimator for details.

4.2.8.4 Primary Analysis of Secondary Endpoint

See Section 4.2.5.4 for details on the statistical inference, hypothesis testing and presentation.

4.2.8.5 Supplementary Analyses of the Secondary Endpoint

A supplementary analysis for change from baseline in log-transformed IL-6 at 16 weeks will be evaluated under the third supplementary estimand defined in Section 4.2 using ANCOVA. See Section 4.2.5.4 for details.

In addition, the following two exploratory analyses will be performed to investigate impact of LLoQ frequency on IL-6 analyses:

- A logistic regression model with the dichotomous response variable derived in Section 4.2.8.2 and treatment group, neutrophil count stratum and baseline IL-6 value as covariates will be used to compare the active treatment groups with placebo. The observed number and proportion of subjects in the below or equal to and over LLoQ for IL-6 respectively, and odds ratios comparing active treatment groups against placebo along with 2-sided 95% confidence intervals and p-value will be presented.

- An analysis using ANCOVA as specified in using only subjects with either hsIL-6 data (using hs lab test or reflex test for high values) at both baseline or 16 weeks, or IL-6 (using standard lab test) at both baseline or 16 weeks will be performed with model specification and presentation as described in Section 4.2.5.4, with the addition of a binary lab test covariate to the model.

